3.3.6 Mixed Model: Terms and Estimation

The form of the linear mixed effects model employed in the analyses in this study is as follows:

$$\ln (SK \ level)_{ij} = X_{ij}\beta + Z_ib_i + \varepsilon_{ij}$$

where:

- 1. $\ln (SK \, level)_{ij}$ is the S-K level in the natural log scale for the j^{th} measurement for the i^{th} subject.
- 2. X_{ij} is the matrix of fixed effects covariates.
- 3. β is a vector containing the fixed-effects regression coefficients.
- 4. Z_i represents the random effects covariates.
- 5. b_i is a normally distributed random effect parameter.
- 6. ε_{ii} is a normally distributed random error term.

Variance components will be estimated using a restricted maximum likelihood method (REML) and an unstructured marginal covariance structure will be assumed. If the specified model fails to converge, the final covariance structure will be determined by Akaike's information criteria: Toeplitz, first-order autoregressive and compound symmetry. The Kenward-Roger approximation will be used to estimate denominator degrees of freedom.

For the analysis of primary endpoint, the model will include S-K data values (natural log scale) assigned to the scheduled visits between Days 8-29 as response variables, and the following fixed effects: eGFR baseline, OLP and RTP baseline S-K values, visit, treatment, visit-by-treatment interaction, as well as age (<55, 55-64, >64 years) and baseline binary indicators for renin-angiotensin-aldosterone system (RAAS) inhibitors, chronic kidney disease, heart failure, and diabetes mellitus.

3.3.7 Multiplicity/Multiple Comparisons

A sequential closed testing procedure will be used in OLP and RTP to maintain an overall Type I error rate of 5%.

Treatment testing will proceed from high dose (ZS 10g) to low dose (ZS 5g) relative to placebo, with statistical significance (two-sided p-value ≤ 0.05) required for the high dose vs. placebo control in order to proceed to the low dose vs. placebo control.

P-values for tests not included in the sequential closed testing procedure are not adjusted for multiplicity and will not be called significant and are considered exploratory.

Specifically, the following fixed hierarchical sequence will be employed: progression to the next test in the sequence will continue until a 2-sided p-value of > 0.05 is encountered, at which any point further testing will cease. Explicitly, Table 3 will be implemented.

D9480C00001 - ed. 3.0

Table 3. Overview of the variables/endpoints and multiplicity testing order

	Endpoints/Variables	Phase	Treatment Comparison	Testing Order in Hierarchy
N	Mean serum potassium [S-K] level		ZS 10g QD vs. Placebo	2
naı	Mean serum potassium [S-K] level		ZS 5g QD vs. Placebo	3
Prin				
	Proportion of subjects who remain normokalemic ^{iv} at the end of RTP ⁱⁱⁱ		ZS 10g QD vs. Placebo	4
	Proportion of subjects who remain normokalemic at the end of RTP	RT	ZS 5g QD vs. Placebo	5
y.	Number of days that subjects are normokalemic		ZS 10g QD vs. Placebo	6
dar	Number of days that subjects are normokalemic		ZS 5g QD vs. Placebo	7
OU	Time to hyperkalemia ^v		ZS 10g QD vs. Placebo	8
Sec	Time to hyperkalemia		ZS 5g QD vs. Placebo	9
	Mean serum potassium [S-K] change from baseline after first dose	OLP	NA	1

ⁱ OLP refers to the 24 or 48 hours Open Label Phase.
 ⁱⁱ RTP refers to the 28 days Randomized Treatment Phase, and Days 8-29 is of interest for the endpoints.
 ⁱⁱⁱ End of RTP in the maintenance day refers to the planned day of last dose of study treatment, Day 29.
 ^{iv} Normokalemic/Normokalemia is defined as having [S-K] level within the range of 3.5-5.0 mmol/L, inclusive.

^v Hyperkalemia is defined as having [S-K] level greater equal than 5.1 mmol/L.

3.3.8 Handling of Protocol Deviations in Study Analysis

There is no defined Per Protocol population for this study and all efficacy analyses will be based on the FAS. Therefore, protocol deviations will not imply exclusion from analyses.

According to ICH E3 (ICH 1995) guidelines,

"Protocol deviations consist of any change, divergence or departure from the study design or procedures defined in the protocol. Important protocol deviations (IPDs) are a subset of protocol deviations that may significantly affect the completeness, accuracy, and/or reliability of the study data or that may significantly affect a subject's rights, safety or well-being."

Important protocol deviations relating to subject-level and subject-visit level events are defined in the Non-Compliance Handling Plan and presented in Appendix A: IPD Master List. They will be reviewed by appropriate medical, clinical, data management, and statistical personnel and will be documented prior to database lock.

A full list of subject inclusion and exclusion criteria is provided in the study protocol.

3.3.9 COVID-19 Impact

If a study participant is unable to attend more than two consecutive clinic visits either due to quarantine for being infected with or suspected for COVID-19 or due to site closure for COVID-19, the investigational product should be discontinued after discussed with AZ.

4 STATISTICAL ANALYSIS

This section provides information on definitions, derivation, and analysis/data presentation per domain.

For all domains, descriptive statistics presented will depend on the type of variable analyzed and will include n (number of subjects included in the analysis), mean, standard deviation (SD), median, minimum and maximum. For categorical variables, they will consist of the number of observations in the respective category, as well as the corresponding percentages.

4.1 Study Population

The domain study population covers subject disposition, analysis sets, protocol deviations, demographics, baseline characteristics, medical history, prior and concomitant medications, and study drug compliance.

The majority of the presentations in this domain, with the exception of the overview of the analysis sets and recruitment, will consist of summary statistics provided for each of the treatment arms, and for the treatment arms combined.

4.1.1 Subject Disposition and Completion Status

4.1.1.1 Definitions and Derivations

Subject accounting will be provided for but not limited to the following:

- Subjects included in the OLP
- Subjects included in the RTP
- Non-randomized subjects
- Subjects who received treatment in the OLP and in the RTP
- Subjects who were randomized but did not receive any treatment in RTP
- Subjects who completed treatment in the OLP
- Subjects who discontinued treatment in the OLP
- Randomized subjects who completed treatment in the RTP
- Randomized subjects who discontinued treatment in the RTP
- Randomized subjects who completed the study
- Randomized subjects who withdrew from the study
- Randomized subjects who discontinued treatment due to global/country situation
- Randomized subjects who withdrew from the study due to global/country situation

4.1.1.2 Presentation

The number and percentage of subjects in the above categories will be presented separately for OLP and RTP.

The subject recruitment will be presented by center for each treatment group.

Disposition listings will include subject ID, age, gender and race, and will be presented sorted by treatment group, subject ID, and date/time of observation.

4.1.2 Analysis Sets

4.1.2.1 Definitions and Derivations

Refer to Section 3.2 for definition of analysis sets.

4.1.2.2 Presentation

The number of subjects included in the FAS and SAF for OLP and RTP, along with the reasons for exclusion from either of the analysis sets where relevant, will be summarized.

A listing of subjects excluded from any analysis set will include subject ID, age, gender and race, and will be presented sorted by treatment group, subject ID, and date/time of observation.

4.1.3 **Protocol Deviations**

4.1.3.1 Definitions and Derivations

Refer to section 3.3.7 for definition of protocol deviations.

4.1.3.2 Presentation

Important protocol deviations will be listed and summarized separately for the FAS-OLP and FAS-RTP.

The number and percentage of subjects with any IPD will be summarized for each IPD category. Subjects with more than one deviation in the same IPD category will be counted once for that IPD category. Any subjects who have deviations in more than one IPD category will be counted once in the overall summary.

The number and percentages of subjects within each important protocol deviation type will be summarized by study phase, OLP and RTP, respectively. In the RTP, summaries will be presented overall and by treatment group. All individual subjects with important protocol deviations will be listed as well for OLP and RTP, respectively.

Similarly, COVID-related IPD will be summarized.

4.1.4 **Demographics**

4.1.4.1 Definitions and Derivations

Demographics are comprised of age, age group, sex, race and ethnicity.

4.1.4.2 Presentation

Demographics will be listed for all subjects enrolled and summarized respectively for the FAS-OLP and FAS-RTP. This listing will include subject ID, age, gender, ethnicity and race, and will be presented sorted by treatment group and subject ID.

In addition to being summarized as a continuous variable, age will be summarized as the age group categorical variable (<55, 55–64, >64 years).

4.1.5 **Baseline Characteristics**

4.1.5.1 **Definitions and Derivations**

Baseline characteristics include height (m), weight (kg) and BMI (kg/m²), baseline serum potassium (S-K), baseline eGFR, baseline binary indicators for RAAS, chronic kidney disease, heart failure and diabetes mellitus.

Baseline parameters are measured/collected up to 1 day prior to administration of the 1st dose of study drug on the open-label initial phase Day 1 (Visit 3).

BMI is calculated as: Weight $(kg) / [Height (m)]^2$.

eGFR will be calculated using the Chronic Kidney Disease Epidemiology Collaboration (CKD-EPI) equation (Levey et al 2009) for each time-point where creatinine is measured, using central laboratory creatinine:

 $eGFR = 141 * min(S_{Cr}/K, 1)^{\alpha} * max(S_{Cr}/K, 1)^{-1.209} * 0.993^{Age} * 1.018$ * 1.159 [if patient is black]

Where:

- 1. S_{Cr} is the standardized serum creatinine in mg/dL
- 2. K = 0.7 (females) or 0.9 (males)
- 3. $\alpha = -0.329$ (females) or -0.411 (males)
- 4. Age is in years.

4.1.5.2 Presentation

Baseline characteristics will be listed for all subjects enrolled and summarized respectively for the FAS-OLP and FAS-RTP. This listing will include subject ID, age, gender and race, and will be presented sorted by treatment group and subject ID.

4.1.6 Medical History and Concomitant Disease

4.1.6.1 Definitions and Derivations

Medical and surgical history are collected up to one day prior to administration of study drug on Day1 (Visit 3) are classified according to the terminology of the latest version of the Medical Dictionary for Regulatory Activities (MedDRA).

4.1.6.2 Presentation

Medical history and surgical history are grouped by MedDRA system organ class and preferred term and are summarized by System Organ Class (SOC) and Preferred Term (PT), for all subjects in FAS-OLP and in FAS-RTP.

They will be listed for all subjects enrolled and summarized respectively for the FAS-OLP and FAS-RTP. This listing will be presented sorted by treatment group, subject ID, and date/time of the event.

4.1.7 **Prior and Concomitant Medications**

4.1.7.1 **Definitions and Derivations**

Medications will be classified according to the latest version of the WHO Drug coding dictionary. Prior medication is any medication that started and stopped prior to treatment with investigational product. Concomitant medication is any medication that is taken concurrently with investigational product regardless of the start date of the medication. Concomitant medications include allowed and disallowed medications taken by the subjects during the respective phases (i.e. a medication can be concomitant for the OLP but not RTP, or RTP but not OLP). Missing medication start and stop dates will be imputed according to Section 3.3.1.4.

For the definition of disallowed medications, see Appendix B.

4.1.7.2 Presentation

Prior and concomitant medications (allowed and disallowed) and procedures will be listed respectively for all subjects in the SAF-OLP and SAF-RTP, and will be presented sorted by treatment group and subject ID.

Concomitant medications and procedures listed in Section 7.7 of the CSP will be summarized by chemical subgroup (ATC 4th level) and preferred WHO name respectively for the SAF-OLP and SAF-RTP. Subjects with the same concomitant medication/procedure multiple times will be counted once per medication/procedure. A medication/procedure that can be classified into more than one (chemical and/or therapeutic) subgroup will be presented in each subgroup. A medical review may also be done.

Disallowed medications will be similarly summarized, separately.

4.1.8 Study Drug Compliance

4.1.8.1 **Definitions and Derivations**

Treatment compliance is obtained by summing up the total number of sachets taken and dividing it by the expected number of sachets to be taken, multiplied by 100%, where the expected number of sachets is calculated over the subject's actual duration in the trial and not the planned duration. Subjects who did not receive IP will have their treatment compliance set to missing.

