• To evaluate the safety and tolerability profiles of ZS in both the open-label initial phase and the 28-day randomized treatment study phase.	 Adverse events (AEs), serious AEs (SAEs), vital signs (VS), physical examinations. ECG Clinical laboratory evaluations, including assessment of hypokalemia. 	

Target patient population

The target patient population includes male or female patients aged ≥ 18 to ≤ 90 years with hyperkalemia, defined as two consecutive i-STAT potassium values, measure 60-minutes apart, both ≥ 5.1 mmol/L within 1 day of the first ZS dose.

Duration of treatment

The study may start with an optional Pre-screening visit. Patients with i-STAT potassium value is equal or more than 5.1 mmol/L will enter the screening. The study will follow with a screening period, and all baseline parameters should be measured/collected up to 1 day prior to administration of first dose of study drug on the open-label initial phase Day 1.

During the open-label initial phase, patients will receive ZS per os (PO) at a dose of 10g three times a day (tid) for 24 or 48 hours, depending on potassium value. Once normokalemia (i-STAT potassium between 3.5 and 5.0 mmol/L, inclusive) is restored (whether after 24 or 48 hours, i.e., by the morning of Study Day 2 or Day 3), patients will then be randomized in a ratio of 2:2:1 to the double-blind 28-day randomized treatment study phase to receive ZS 5g, 10g or placebo, PO qd for the following 28 days. Patients in the double-blind treatment phase will be required to complete the Day 29 visit and the EOS visit which is 7 ± 1 days after the last administration of study medication. For patients who do not enter the 28-day randomized treatment study phase the last visit will be 7 ± 1 day after the last treatment dose in the open-label initial phase. The total expected study duration for each individual patient is approximately 5-6 weeks.

Investigational product, dosage and mode of administration

Open-label initial phase:

• ZS 10g will be administered orally three times a day (tid) for 24 or 48 hours as an oral suspension.

28-day randomized treatment study phase:

- ZS 5g will be administered orally once daily (qd) for 28 days as an oral suspension.
- ZS 10g will be administered orally once daily (qd) for 28 days as an oral suspension.
- Matching Placebo for ZS will be administered orally once daily (qd) for 28 days as an oral suspension.

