3.6 Methods for ensuring blinding

The 28-day randomized treatment study phase will have a double blind design. Patients will take by mouth the entire contents of a single sachet qd, containing either ZS 5g, ZS 10g or placebo. The exterior of the sachets are identical. Individual sachets are enclosed in a carton with a tamper evident seal intended to be broken exclusively by patients just before taking the study drug.

No member of the study team at AZ, or representative, personnel at study centers or any clinical research organization (CRO) handling data will have access to the randomization scheme during the conduct of the study, with the exception of the AZ personnel generating the randomization scheme as well as AZ Supply Chain, the Patient Safety data entry site and the CRO companies providing the IVRS/IWRS and carrying out the packaging and labeling of study medication. This documentation will be kept in a secure location until the end of the study.

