 - An absolute QTc >550msec, or an increase in QTc interval > 60msec from baseline to more than 500msec. All patients meeting the QTc>500ms criterion should immediately have potassium assessed by i-STAT and central lab, if not already done within 1 hour of the collection of the ECG. The QTc(f) algorithm (QT interval corrected by the Fridericia method) is recommended.

Patients who discontinue from study medication during the 28-day randomized treatment study phase but agree to remain in the study should continue to follow protocol-specified procedures and assessments except for dispensing of study medication for the study.

Any patient who is discontinued from the study treatment during open-label initiation phase will return to the clinic 7 (\pm 1) days after the last IP administration for an EOS visit. Note: Discontinuation of investigational product does not necessarily imply discontinuation of follow-up or termination of all study participation.

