If a patient develops i-STAT potassium values between 3.0 mmol/L and 3.4 mmol/L, inclusive (confirmed by taking a second potassium measurement after a 10 ± 2 minute interval), during the 28-day randomized treatment study phase, dosing will be reduced from qd to qod for the remainder of the study.

Patients with confirmed potassium <3.0 mmol/L in both study phases should discontinue from therapy as per Section 3.9.

Patients with confirmed i-STAT potassium >6.2 mmol/L during the 28-day randomized treatment study phase should discontinue from therapy as per Section 3.9.

For doses administered in the clinic during both study phases each dose will be individually dispensed by designated, trained site staff.

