4.1.8.2 Presentation

Treatment compliance will be summarized separately for the OLP and the RTP, overall and by treatment group.

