4.3.1 Exposure

4.3.1.1 Definitions and Derivations

Duration of exposure is defined as the number of days between the first and the last dose of IP + 1 day, for each treatment period. Duration of exposure for subjects on every other day dosing is defined as the number of days between the first and the last dose of IP where subjects have a planned dose of IP + 2 days.

Actual Exposure

Actual exposure for each subject will be obtained by summing up the days for which at least one dose of the drug was taken, excluding dose interruptions, and for each treatment arm and overall.

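### SAP 4.1.8.1 counts expected sachets over time in the trial rather than time on drug, and does not say whether the count follows every-other-day dosing or holds, so compliance can be understated

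*SAP*

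**What the plan says.** SAP 4.1.8.1 gives the ratio: "Treatment compliance is obtained by summing up the total number of sachets taken and dividing it by the expected number of sachets to be taken", times 100. On the time base it adds that "the expected number of sachets is calculated over the subject's actual duration in the trial and not the planned duration". It does not say which dosing schedule defines an expected sachet. SAP 4.1.8.2 states the output: "Treatment compliance will be summarized separately for the OLP and the RTP, overall and by treatment group".

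Three protocol rules bear on the denominator.

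- **Stopping drug.** Under Protocol 3.9, patients who stop drug in the randomized phase and "agree to remain in the study should continue to follow protocol-specified procedures", with dispensing as the exception. Protocol 3.10 treats withdrawal from the study as a separate event.
- **Dose reduction.** Under Protocol 7.2, after a confirmed i-STAT potassium of 3.0-3.4 mmol/L in the randomized phase, "dosing will be reduced from qd to qod for the remainder of the study".
- **Open-label hold.** Under Protocol 7.2, the same potassium range in the open-label phase means that the rest of that day's doses are withheld.

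The exposure section, SAP 4.3.1.1, does provide for the reduced regimen. It has a separate rule beginning "Duration of exposure for subjects on every other day dosing is defined as", and its count of actual exposure leaves out interruptions.

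**The concern.** Time in the trial and time on drug are different periods in this protocol. If the denominator covers the first, sachets remain expected on days when none is dispensed. A patient who followed the stopping rules exactly then gets a low percentage. A similar problem arises if a daily schedule is assumed for a patient moved to every-other-day dosing.

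On that daily-schedule reading the measure can even run backwards. A patient who should have been reduced but stayed on daily dosing scores 100%, although SAP Appendix A lists this as important protocol deviation 5.4. A patient who was reduced as required scores less.

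Efficacy is analysed under a treatment-policy approach that keeps data after discontinuation. Readers may therefore look to the by-arm compliance table to judge how closely assigned dosing was followed. A figure that mixes missed doses with protocol-directed changes answers that poorly. Two programmers could also derive different values from the same text.

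**Working it through.** The documents state no compliance figure, so there is none to reproduce. The check applies the SAP ratio to patients who take every sachet they are prescribed.

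**Inputs**

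- Randomized phase: "the entire contents of a single sachet qd" (Protocol 3.6). The synopsis gives the length: "Matching Placebo for ZS will be administered orally once daily (qd) for 28 days as an oral suspension". That makes 28 planned sachets, Days 1-28.
- Open-label phase: three doses a day, at most six (Protocol 7.2).
- Assumptions: a change or stop takes effect at a scheduled visit before that day's dose, and the patient stays through the dosing period.

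**Stop at Day s, patient remains to Day 29.** Taken = s − 1. Literal denominator = 28.

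- s = 8: 7/28 = 25.0%
- s = 15: 14/28 = 50.0%
- s = 22: 21/28 = 75.0%

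**Every-other-day dosing from Day s, daily schedule as denominator.** Taken = (s − 1) + half of the remaining 28 − (s − 1) days, rounded down or up according to which day the alternation starts.

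| s | Before | Remaining days | Taken | Score |
|---|---|---|---|---|
| 8 | 7 | 21 | 17-18 | 60.7-64.3% |
| 15 | 14 | 14 | 21 | 75.0% |
| 22 | 21 | 7 | 24-25 | 85.7-89.3% |

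The earliest case, from Day 2, gives 14-15 of 28, or 50.0-53.6%.

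**Open-label hold, full three-a-day schedule as denominator**

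- Held on Day 1 after the first dose, randomized on Day 2: 1/3 = 33.3%
- Held on Day 2 before dosing: 3/6 = 50.0%

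**Denominator based on the regimen in force while on drug.** Every case above becomes 100%.

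**Effect on an arm mean.** Shift = share affected × (100 − score). The documents give no rate for reduction to every-other-day dosing. Protocol 1.3.2 gives hypokalemia (below 3.5 mmol/L) in 4.1% of ZS patients, used here as an assumed share.

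- Early reduction, 14/28: 0.041 × 50.0 = 2.05 points
- Day 8, 17/28: 0.041 × 39.3 = 1.61 points
- Day 22, 25/28: 0.041 × 10.7 = 0.44 points

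The range is about 0.4-2.1 points. For stops with continued follow-up the documents give no rate, so no arm-level figure is offered.

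**The case against.** The best defence is that a sachet expected to be taken is naturally a sachet prescribed. On that reading a patient on every-other-day dosing or under a hold scores 100%, and nothing is wrong. This stands in part: for the reduction and the hold, the SAP is silent rather than wrong. It is weaker for drug stops, because the SAP names time in the trial as the basis for the count, and the protocol deliberately keeps that time separate from time on drug.

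A strictly literal reading also looks unintended. If time in the trial ran to the end-of-study visit at Day 35, a patient who took all 28 sachets would score 28/35 = 80%. The clause was probably meant to avoid penalising shorter participation. That speaks to intent, but it also shows that the wording needs correcting.

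Several stronger inferences are tempting, and the documents do not support them.

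- *Rule-following patients are labelled non-compliant.* SAP 4.1.8.2 only summarizes a percentage. There is no cut-off or category.
- *Compliance is the only view of dosing.* SAP 4.3.1 summarizes duration of exposure and actual exposure, SAP 4.1.1 tabulates treatment discontinuation, and deviations 5.3-5.5 in Appendix A cover dose adjustments.
- *About 10 in 100 patients on 10 g is an upper limit for those affected.* Figure 2 of the protocol shows a hypokalemia excess of 9.8 points, but its interval is 1.6 to 18, so it is not a bound. Neither it nor the 4.1% is tied to the confirmed i-STAT trigger.
- *The arm comparison is known to be distorted.* Reductions for low potassium plausibly fall on ZS and stops above 6.2 mmol/L on placebo, so the two may partly offset. No rate is given for the stops.

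**Conclusion.** The point holds as a minor correction with two parts of different strength. The time base is wrong as written: read literally, it keeps counting sachets after drug has stopped, and a patient who took every prescribed sachet scores 25% (stop at Day 8) or 50% (stop at Day 15). The treatment of every-other-day dosing and open-label holds is an ambiguity. It yields 61-64%, 75% or 86-89% for reduction at Day 8, 15 or 22 only if the daily schedule is used.

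The consequence is confined to the descriptive compliance table. SAP 3.3.8 defines no per-protocol set and excludes no one for deviations, and no efficacy analysis uses compliance. The arm-mean effect of about 0.4-2.1 points covers dose reductions only. It rests on the assumed 4.1% share and on when reductions occur.

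**What to change.** In SAP 4.1.8.1, replace the reference to time in the trial with the period from first dose to the earlier of planned end of dosing or permanent drug discontinuation in that phase. State that expected sachets are counted on the regimen in force each day under the protocol (three times daily, daily, every other day, or held), consistent with SAP 4.3.1.1. For every-other-day dosing, also state the day from which the alternation is counted, since that alone moves the count by one sachet.

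The cost is SAP wording and programming. The exposure derivations already need dosing dates and every-other-day status.

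There is one downside. A patient who stops by choice is then scored only up to the stop and could show 100%. The table should therefore be read with the discontinuation summary already planned in SAP 4.1.1.
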